3.2 Analysis Populations

Patients treated without or before being randomized will not be considered randomized and will not be included in any analysis populations

3.2.1 *Randomized Population*

The Randomized Population is defined as all patients who were randomized.

3.2.2 *Intent-to-Treat (ITT) Population*

The ITT Population includes all patients who are randomized and administered at least 1 dose of study drug.

3.2.3 *Safety Population*

The Safety Population includes all patients who are randomized and administered at least 1 dose of study drug.

3.2.4 *Modified ITT Population*

The Modified ITT (mITT) Population includes patients from the ITT Population who have valid baseline and Week 12/ET MRI-PDFF measurements of LFC.

3.2.5 *Per-Protocol Population*

The Per-Protocol Population includes all patients from the mITT Population without any major protocol violations. The analysis of LFC as measured by MRI-PDFF will be repeated on the Per-Protocol Population to test the robustness of results.

A major protocol violation is defined as any CSR reportable protocol deviation likely to affect the primary efficacy endpoint including the following categories (see Protocol Deviation Plan for further details):

- A patient that did not meet entry criteria;
- A patient that developed withdrawal criteria but were not withdrawn;

- A patient that received the wrong treatment or incorrect dose;
- A patient that received an excluded medication
- A patient that has less than 50% of morning compliance (part A) or less than 60% overall compliance (part B).

All patients with a CSR reportable protocol deviation will be reviewed and assessed for inclusion into the Per-Protocol Population; this review will be carried out by the Sponsor and Medical Monitor and agreed upon prior to the first database lock.

Excluded medications are detailed in the Protocol Section 5.6.1 Excluded Medications and/or Procedures (3rd and 4th bullet) that may have an effect on the primary efficacy endpoint:

- Vitamin E (>400 IU/day), glitazones, glucagon-like peptide-1 receptor agonists, ursodeoxycholic acid, or obeticholic acid within 90 days prior to screening
- Agents (including herbal over-the-counter weight loss preparations) or medications known to significantly impact body weight within 90 days prior to screening (e.g., sibutramine, phenetamine, and orlistat).

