3.7 Safety Assessment

The safety data for this study include AEs, pruritus assessments, safety laboratory assessments, vital signs and anthropometrics, ECGs and physical examinations. The safety data will be summarized based on the Safety Population and presented by treatment group. Missing values will not be imputed. All reported safety data will be listed for the Randomized Population.

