3.7.1 Adverse Events (AEs)

An AE is defined as any untoward medical occurrence in a clinical investigation patient administered a pharmaceutical product, which does not necessarily have a causal relationship with this treatment. An AE can therefore be any unfavorable and/or unintended sign (including an abnormal laboratory finding), symptom, or disease temporally associated with the use of an investigational medicinal product, whether or not related to the investigational medicinal product.

For analysis, a treatment emergent AE (TEAE) is defined as a new or worsening AE after the first dose of study drug. Programmatically, this will be identified as any AE with a start date on or after the date of first dose. If part of the date for the onset/end of an AE is missing, but the existing parts allow determination of timing of AE onset relative to the first dose of study drug, then the AE will be classified as treatment-emergent or not per review of the existing parts of the date. If timing of the AE onset/end relative to the first dose of study drug cannot be determined, then the AE will be assumed to be treatment-emergent.

A summary overview of all AEs will be provided, which presents the number and percentage of patients in each treatment group from the Safety Population, including number of events, satisfying each of the following categories:

- Any AE
- Any TEAE
- Maximum severity of TEAEs
- Study drug-related TEAEs
- Maximum severity of study drug-related TEAEs
- TEAEs of special interest:
 - Part A: pruritus, Drug Induced Liver Injury (DILI) and muscle-related

➤ Part B: elevation of transaminases and muscle-related

- All serious AEs (SAEs)
- All serious TEAEs (TESAEs)
- All study drug-related TESAEs
- TEAEs leading to early discontinuation
- TEAEs leading to temporary discontinuation of study drug
- TEAEs leading to dose reduction

AEs will be coded using MedDRA v22. The number and percentage of patients with AEs, including the number of AEs, will be summarized by their MedDRA preferred term within system organ class and treatment group. For patient count summaries, multiple AE events with the same MedDRA coded terms (preferred term and system organ class) from the same patients will only be counted once. Similar summaries will be presented for study drug-related TEAEs and TESAEs.

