The number and percentage of patients with TEAEs will be summarized by reported maximum severity within each MedDRA preferred term within system organ class and by treatment group.

A further summary table for TEAEs by preferred term and system organ class will be provided for patients in the Safety Population who were taking a statin; a separate summary table will be provided for patients in the Safety Population who were not taking a statin. Patients who were and were not taking a statin will be identified from the appropriate stratification variable.

Detailed listings will be provided for all AEs. Separate listings will also be provided for AEs of Special Interest, SAEs, TEAEs leading to early discontinuation, TEAEs leading to temporary discontinuation of study drug and TEAEs leading to dose reduction.

For both Part A and Part B, an additional summary of derived pruritus TEAEs will be provided for the following categories:

- Grade 1 (mild or localized), defined as (severity grade 1 and (flagged as pruritus AESI on the eCRF or preferred term="Pruritus generalised")) or preferred term = "Pruritus"
- Grade 2 (widespread and intermittent), defined as severity grade 2 and preferred term = "Pruritus generalised"
- Grade 3 (widespread and constant), defined as severity grade 3 and preferred term = "Pruritus generalised"

3.7.2 *Pruritus Assessments*

Part A

The pruritus visual analog scale (VAS) and 5-D (degree, duration, direction, disability and distribution) itch scale will be assessed at Days 1, 7, 14, 21, 28, 56, 84 and 98 and also at the ET Visit.

Descriptive statistics for the pruritus VAS and 5-D itch scale will be presented for baseline values and for values and the change from baseline at each post-baseline visit.

Part B

In Part B, pruritus will be reported as any other AE. If a patient reports pruritus, the visual analog scale and the 5-D questionnaire (degree, duration, direction, disability, and distribution) itch scale will be administered. Results will be listed.

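### If a patient is dosed without or before randomisation, SAP 3.2 removes them from the Safety Population, so their adverse events reach no safety table and, under SAP 3.7, no safety listing

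*SAP*

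**What the plan says.** Under the opening rule of SAP 3.2, anyone who takes study drug without randomisation, or ahead of it, is not counted as randomised, and such patients "will not be included in any analysis populations". The definitions beneath it fit that rule. "The Randomized Population is defined as all patients who were randomized", and "The Safety Population includes all patients who are randomized and administered at least 1 dose of study drug", so receiving drug is not enough for entry to the Safety Population.

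SAP 3.7 assigns the outputs. For tables: "The safety data will be summarized based on the Safety Population and presented by treatment group". For listings: "All reported safety data will be listed for the Randomized Population". SAP 3.7.1 repeats the table population for the adverse event overview, "which presents the number and percentage of patients in each treatment group from the Safety Population", and adds "Detailed listings will be provided for all AEs" without naming a population. SAP 3.3.2 limits the summary and listing of reportable protocol deviations to the Randomized Population. SAP Section 6 says in general terms that all available data will go into patient listings, again with no population named.

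Protocol 10.1 makes the Safety Population identical to ITT, that is, randomised and given at least one dose. It has no rule about the order of dosing and randomisation.

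**The concern.** Leaving these patients out of ITT, mITT and Per-Protocol protects the randomised comparison. That reason does not carry over to safety, where the question is what happened to people who were exposed. As written, the result is inverted: a patient randomised and never dosed belongs in the safety listings, while a patient who took drug does not.

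The drug has a hepatic question still open. Protocol 1.2.2 reports two Grade 3 and one Grade 2 transaminase elevations in Part A, and Protocol 1.2.3 does not rule out a causal link. With about 30 patients per arm in Part B, the report should account for every exposed patient.

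**Working it through.** The plan states no figure to reproduce. The check is to follow one hypothetical patient through the population rules and then to bound the effect on an event rate.

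**Tables and listings.**
1. A patient takes study drug without being randomised, or before it. Under SAP 3.2 the patient is treated as not randomised.
2. Both the Safety definition and the blanket exclusion then keep the patient out of the Safety Population. Under SAP 3.7 and 3.7.1 the patient is in no safety table.
3. The patient is also outside the Randomized Population. Under SAP 3.7 the patient is in no safety listing. The all-AE listing in SAP 3.7.1 sits under that rule.
4. Under SAP 3.3.2 the dosing error itself would also be missing from the deviation summary and listing.
5. SAP Section 6 points the other way on listings. It is general, whereas SAP 3.7 is specific to safety, so the two conflict and need reconciling. It does not affect step 2.

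**Protocol against SAP.**

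| Patient | Protocol 10.1 Safety (= ITT) | SAP 3.2 Safety |
|---|---|---|
| Dosed, never randomised | Outside | Outside |
| Dosed first, randomised later | Meets the definition | Excluded |

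Only the second row is a change made by the SAP. SAP Section 5, which lists departures from the protocol, does not mention it.

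**Size.** Take x events among n patients in an arm, with one dosed patient left out.
- If the omitted patient had the event, restoring them moves the rate by (x + 1)/(n + 1) − x/n = (n − x)/[n(n + 1)].
- If not, it moves by x/(n + 1) − x/n = −x/[n(n + 1)].
- Either way the shift cannot exceed 1/(n + 1).

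With n = 30 (Protocol 3.1 plans about 30 per arm):
- Omitted patient has the only event: 0/30 becomes 1/31 = 3.2%, a shift of 3.2 points. If the patient is one of the planned 30, the comparison is 0/29 with 1/30, or 3.3 points.
- Common event, taking 60% as an illustration (the Part A pruritus rate at 200 mg QD in Protocol 1.2.2, 3 of 5), so x = 18: with the event, 18/30 = 60.0% becomes 19/31 = 61.3%, up 1.3 points. Without it, 18/31 = 58.1%, down 1.9 points.
- The bound is also reached in the mirror case, where every other patient in the arm had the event and the omitted one did not.

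**The case against.** The strongest reply is that the data are not lost and the event should not happen. Adverse events are recorded, and SAEs reported, from informed consent whatever the randomisation status (Protocol 9.1 and 9.3). In Part B the DSMC is notified of liver elevations in any patient (Protocol 10.2.7). The final database holds all screened patients (SAP 4.2). Randomisation runs through IRT and must precede dosing on Day 1 (Protocol 5.3.1 and 6.3.3.1), and drug is packaged to the randomisation schedule (Protocol 5.5.1). No case is reported. All of this stands, and it confines the point to the planned analysis outputs and to a protocol breach.

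A reader might infer three stronger things, none of which the documents support:
- That an SAE in such a patient would go unreported. SAE reporting does not depend on the analysis populations.
- That the patient would certainly be in no listing at all. SAP Section 6 contradicts SAP 3.7 here, so only the absence from tables is beyond dispute.
- That one omitted patient shifts every event rate by 3.3 points. That is close to the upper bound, and common events such as the 60% example shift by much less.

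It is also fair to say that the SAP is not the sole source. For a patient never randomised it only repeats what Protocol 10.1 already implies.

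None of this justifies keeping a known exposed patient out of the safety tables.

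**Conclusion.** The point holds as a minor one. If such a dosing error occurs, the plan as written keeps the patient's adverse events out of every safety table and, under SAP 3.7, out of every safety listing, with SAP Section 6 in conflict on the listings. For patients dosed first and randomised later, the SAP narrows the protocol's Safety Population without recording the change.

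The effect on an arm's event rate is at most about 3 percentage points for one patient. That figure assumes an arm of about 30, a single omitted patient, and a patient who can be attributed to an arm. If no such patient exists, no result changes.

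**What to change.** Amend the SAP as follows:
- **3.2:** define the Safety Population as all patients who received at least one dose, summarised by actual treatment. SAP 3.1.1 already allows presentation by actual treatment. A patient whose actual treatment cannot be established should be listed separately. Limit the exclusion to the Randomized, ITT, mITT and Per-Protocol Populations.
- **3.7 and 3.3.2:** list safety data and protocol deviations for the Randomized Population plus all dosed patients, flagging those dosed without or before randomisation.
- **3.7 and 6:** reconcile the two statements on listings.
- **5:** record the change.

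The cost is a few lines of SAP wording and a documented departure from Protocol 10.1, since Safety would no longer be identical to ITT. No new data are needed.

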3.3 Subject Data and Study Conduct

3.3.1 *Subject Disposition*

This section describes patient disposition for both patient study status and the patient analysis populations. Note that all screen failures for the entire study will be considered together, i.e. combining screen failures from Part A and Part B.

A patient disposition summary will be provided for the Randomized Population and will include the following categories:

- Patients who were randomized
- Patients who received at least one dose of study drug
- Patients who completed the study
- Patients who withdrew from the study (and reasons for withdrawal)
- Patients whose primary reason for withdrawal was non-compliance due to COVID-19

Disposition events during the screening period will be summarized overall. Disposition events from the Day 1 (Week 0) onwards will be summarized by treatment group and overall.

Reasons for early withdrawal from the study (i.e. withdrawal after randomization) will be summarized by treatment group for the Randomized Population.

A disposition listing containing the randomization details (randomized treatment group and date of randomization), dates of first and last dose of study drug and completion status (with date and reasons for withdrawal for patients who withdrew) will be provided for all patients in the Randomized Population.

3.3.2 *Protocol Deviations*

Counts and percentages of patients with CSR reportable protocol deviations by deviation category will be summarized by treatment group for the Randomized Population. A similar summary will be provided for COVID-19 related CSR reportable protocol deviations.

A listing of CSR reportable deviations will also be produced for the Randomized Population.

Inclusion/Exclusion criteria deviations will also be listed for the Randomized Population.

3.3.3 *Analysis Populations*

Counts and percentages of patients in each analysis population will be summarized by treatment group and in total. Only counts will be displayed for the Randomized Population and the denominator for the other analysis populations will be based on the Randomized Population.

A listing of analysis population inclusion will also be provided.

3.3.4 *Demographic and Baseline Characteristics*

Demographic and baseline characteristics will be summarized with descriptive statistics or counts and percentages of patients as appropriate by treatment group and in total for the ITT Population.

A similar summary will be provided for the mITT Population and Per-Protocol Population if the size of the population is different (>10%) from the size of the ITT Population for any treatment group.

Demographic characteristics include age, gender, ethnicity and race.

Baseline characteristics include:

- Stratification variables – statin use and T2DM status at screening (Part A), statin use and LFC category at screening (Part B);
- LFC as assessed from MRI-PDFF;
- cT1;
- LSM and CAP as assessed by FibroScan;
- Anthropometric parameters – height, weight, BMI and waist circumference, waist to hip ratio (Part B), waist to height ratio (Part B)
- Vital Signs – systolic blood pressure (SBP), diastolic blood pressure (DBP), heart rate (HR), Respiratory Rate and Temperature
- Alcohol use (Alcohol Use Disorders Identification Test-Concise [AUDIT-C] Total Score);
- Biomarkers of liver fibrosis and inflammation;
- Liver Function Tests – ALP, Total Bilirubin, GGT, International normalized ratio (INR) and Albumin.

Stratification variables will be sourced from the value used for randomization stratification, even if it is later found to be incorrect based on the patient data. Mis-stratification will be flagged in the listings.

3.3.5 *Medical History*

Medical history will be coded using the Medical Dictionary for Regulatory Activities (MedDRA) version 22. The number and percentage of patients with medical history will be summarized by

preferred term within system organ class and treatment group for the Randomized Population and presented by descending overall frequency of system organ class, and within system organ class by descending incidence of preferred term

All reported medical history will be listed.

3.3.6 Prior and Concomitant Medications

Prior and concomitant medications will be coded to World Health Organization (WHO) Drug Global B3, Mar-2019. A prior medication is defined as any medication taken by the patient before the first dose of study drug.

A concomitant medication is defined as any medication taken by the patient at the same time or after the first dose of study drug.

If a medication has incomplete start or stop dates, dates will be imputed to determine whether a medication should be considered concomitant or prior. If a medication start date is incomplete, the first day of the month will be imputed for missing day and January will be imputed for missing month. If a medication stop date is incomplete, the last day of the month will be imputed for missing day and December will be imputed for missing month. Incomplete start and stop dates will be listed as collected without imputation.

The number and percentage of patients taking prior and concomitant medications by preferred term within Anatomical Therapeutic Chemical (ATC) Class will be summarized by treatment group and in total based on the Safety Population.

The number and percentage of patients taking a prior or concomitant statin medication will also be summarized for the Safety Population and will include details of the type of statin taken.

All reported prior and concomitant medications, including statin medications, will be listed.

3.3.7 Study Drug Exposure and Compliance

Days of overall exposure to study drug will be summarized by treatment group for the Safety Population using descriptive statistics. Exposure, in days, will be calculated as:

$$\text{date of last dose of study drug} - \text{date of first dose} + 1$$

Note that the exposure calculation is intended to describe the length of time a patient was exposed to study drug and therefore does not take study drug interruptions into account.

If the date of last dose of study drug is missing from the end of treatment electronic Case Report Forms (eCRF), for example if a subject is lost to follow-up, then the last dose of study drug will be imputed for the purpose of calculating exposure and compliance. The details of the imputation will be described in the programming specifications.

In addition, a contingency table will be provided to display the number and percentage of patients with exposure in the following categories:

- ≤ 4 weeks (≤ 28 days)
- > 4 to ≤ 8 weeks (29 - 56 days)
- > 8 to ≤ 12 weeks (57 – 87 days)

Total percent compliance will be calculated as:

$$\frac{\text{Number of tablets taken} \times 100}{\text{Expected number of tablets to be taken}}$$

The number of tablets taken will be derived from the data recorded within the eCRF and will be calculated as the difference in the total number of tablets dispensed and the total number of tablets returned.

In Part A, only returned study drug wallets will be used for the calculation of compliance. In Part B if study drug is not returned, it will be imputed as 0 tablets returned for the purpose of calculating compliance. However if drug is dispensed on or after the date of last dose (such as in the case of a subject lost to follow-up and last dose is imputed), it may be excluded from the compliance calculation.

The expected number of tablets to be taken will be derived from the dates of first and last dose, assuming 3 tablets are taken per day (Part A) or assuming 1 tablet is taken per day (Part B).

The expected number of tablets to be taken will not take into account the duration of any temporary interruption to study treatment (e.g. due to AE).

In Part A, morning percent compliance will be calculated as:

$$\frac{\text{Number of morning tablets taken} \times 100}{\text{Expected number of morning tablets to be taken}}$$

In Part A, the number of morning tablets taken will be derived from the data recorded within the eCRF as the difference in the total number of morning tablets dispensed and the total number of morning tablets returned. The total number of morning tablets dispensed is assumed to be two thirds of the total number of tablets dispensed.

In Part A, the expected number of tablets to be taken will be derived from the dates of first and last dose, assuming 2 tablets are taken in the morning per day.

Total and morning percent compliance with the study treatment will be summarized by treatment group for the Safety Population using descriptive statistics. Additionally, the number and percentage of patients within each treatment group with compliance in the following categories will be provided:

Total percent compliance

- < 80%
- 80 - 120% (inclusive)
- 120%

Morning percent compliance (Part A only)

- < 50%
- 50 - < 80%
- 80 - 120% (inclusive)
- 120%

All reported drug accountability, exposure, and compliance information will be listed.

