5.5 Drug Supplies

5.5.1 Formulation and Packaging

The drug product will be supplied as immediate-release coated tablets for oral administration. Excipients include lactose monohydrate, microcrystalline cellulose, crospovidone, sodium lauryl sulfate, silicon dioxide, and magnesium stearate. Placebo tablets will appear identical to EYP001a.

For Part A, all study drug (EYP001a and placebo) will be packaged in blister packs and wallets. One wallet will contain 2 weeks of study drug (ie, 14 days of EYP001a or placebo) as per the randomization schedule. Morning and evening tablets will be clearly labeled.

For Part B, all study drug (EYP001a and placebo) will be packaged in blister packs and carton boxes. One box will contain 3 weeks of study drug (ie, 3 blister strips or 21 days of EYP001a or placebo) as per the randomization schedule.

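### Part A compliance counts the days of an unreturned wallet as missed doses; this lowers the compliance tables and reaches the Per-Protocol rule only when many wallets are missing

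*SAP*

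**What the plan says.** SAP 3.3.7 defines compliance as tablets taken over tablets expected. Tablets taken are "calculated as the difference in the total number of tablets dispensed and the total number of tablets returned". For Part A it adds: "In Part A, only returned study drug wallets will be used for the calculation of compliance".

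The denominator is defined separately: "The expected number of tablets to be taken will be derived from the dates of first and last dose", at three tablets a day in Part A. Morning compliance follows the same pattern, with its expected count "derived from the dates of first and last dose, assuming 2 tablets are taken in the morning per day". The section does not say that days covered by unreturned wallets leave either expected count. It does say that temporary interruptions stay in.

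For Part B the same section goes the other way: drug that is not returned is treated as if no tablets were left, so it counts as taken.

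The result is used in two places. SAP 3.3.7 tabulates total compliance (below 80%, 80 to 120%, above 120%) and, for Part A, morning compliance with a further cut at 50%. SAP 3.2.5 makes Part A morning compliance below 50% a major violation for the Per-Protocol Population. Patients with reportable deviations are then reviewed by the Sponsor and Medical Monitor.

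On packaging, Protocol 5.5.1 says: "One wallet will contain 2 weeks of study drug".

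**The concern.** The numerator and denominator cover different periods. Intake from an unreturned wallet cannot be observed, yet its days are scored as if no tablet had been taken. The Part A figure therefore depends on whether packaging came back as well as on whether tablets were swallowed, and the error is always downward. Part B errs upward for the same event, so the two parts' compliance figures are not comparable.

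What is at stake is mainly the accuracy of the Part A compliance tables. Membership of the Part A Per-Protocol Population is a secondary matter. Part A has only 24 patients, with 5 to 7 per group according to Protocol 1.2.2, so a single misplaced patient would be visible.

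**Working it through.** The plan gives no compliance figure for unreturned wallets, so there is nothing to reproduce. The check is direct arithmetic.

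**Inputs**
- Part A tablets per day: 3 in total, 2 in the morning (SAP 3.3.7; Protocol 5.1, Table 1).
- One wallet covers 14 days (Protocol 5.5.1): 14 × 3 = 42 tablets, of which 14 × 2 = 28 are morning tablets.
- Full course of 84 days (Protocol 6.5): 84/14 = 6 wallets, 84 × 3 = 252 tablets, 84 × 2 = 168 morning tablets.
- Dispensing at Weeks 0, 2, 4 and 8 (Protocol 5.5.2). I infer 1, 1, 2 and 2 wallets, with returns at Weeks 2, 4, 8 and 12.
- Visit window of ±3 days at Week 12 (Protocol 6).
- Per-Protocol cut-off: morning compliance below 50% (SAP 3.2.5).

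**Formula.** For a patient who takes every tablet over D days, with m fully used wallets not returned:

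total = 3(D − 14m)/(3D) = 1 − 14m/D

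morning = 2(D − 14m)/(2D) = 1 − 14m/D

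Both measures fall by the same amount. At 84 days the loss per wallet is 42/252 = 28/168 = 16.7 points.

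| Days D | Points lost per wallet | 1 missing | 2 missing | 3 missing | 4 missing |
|---|---|---|---|---|---|
| 84 | 16.7 | 83.3% | 66.7% | 50.0% | 33.3% |
| 83 | 16.9 | 83.1% | 66.3% | 49.4% | 32.5% |
| 81 | 17.3 | 82.7% | 65.4% | 48.1% | 30.9% |
| 70 | 20.0 | 80.0% | 60.0% | 40.0% | 20.0% |
| 56 | 25.0 | 75.0% | 50.0% | 25.0% | 0% |
| 42 | 33.3 | 66.7% | 33.3% | 0% | – |
| 28 | 50.0 | 50.0% | 0% | – | – |

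**Compliance categories.** Over 84 days one missing wallet leaves the patient in the 80 to 120% band. Two put the patient below 80%. On the inferred dispensing pattern, that happens if the Week 8 supply alone is not returned.

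**Per-Protocol cut-off.** The rule is strictly below 50%. At 84 days three missing wallets give exactly 50.0%, which is not below, so four are needed (for example, nothing returned at Weeks 8 and 12: 33.3%). With the last dose on Day 81 to 83, three fully used missing wallets give 48.1 to 49.4%. If one of those three is the partly used last wallet, 42 days are still seen and the score is 42/81 = 51.9% to 42/83 = 50.6%, which stays in. With shorter exposure fewer are needed: three at 56 or 70 days, two at 42 or 28 days.

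**With real non-adherence.** If intake is even over 84 days, the recorded value is true adherence times the factor above. A patient at 70% with two wallets missing scores 0.70 × 66.7% = 46.7%. The cut-off is crossed below 75% true adherence with two missing (0.75 × 66.7% = 50%) and below 60% with one missing (0.60 × 83.3% = 50%).

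**After matching the periods.** If the denominator covers only returned wallets, the fully adherent patient scores 100% with 0 to 5 wallets missing. With all six missing the ratio is undefined.

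**The case against.** The returned-wallets sentence speaks of the calculation as a whole, so it can be read as restricting both terms of the ratio. On that reading there is no bias, only loose wording. The reading is possible, but the expected counts are defined explicitly by first and last dose, twice, with no such restriction. A programmer following the text would use all days. Either way one clarifying sentence is needed.

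A reader might infer that a fully adherent patient who loses a wallet or two would be dropped from the Per-Protocol Population. The documents do not support that: over a full course, one to three missing wallets leave 83.3%, 66.7% and 50.0%, none below the cut-off at 84 days. Exclusion also passes through case review, diaries are reviewed for compliance in Part A (Protocol 5.5.4), and accountability data are listed (SAP 3.3.7), so the cause of a low score would be visible. Nor is an early stopper a good example. A fully adherent patient stopping on Day 20 without returning the second wallet scores 42/60 = 70%. Protocol 6.5 requires an early-termination MRI only after at least 4 weeks on drug, so this patient is not expected to be in the mITT or Per-Protocol Population. Only the tables are affected.

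A reader might also infer that past Part A results are wrong, or wrong by arm. This cannot be shown. SAP Section 1 refers to SAP V1.0 for the Part A analysis, V1.0 is not among the documents, and no count of unreturned wallets is given by arm or overall.

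The timing objection stands in part. Protocol 5.4 reports Part A locked and unblinded, and SAP 4.2 fixes population exclusions before unblinding. Re-applying the 50% rule now would redefine a population after results are known. But SAP 4.3 still plans a full set of Part A tables in the final delivery, so correcting the compliance tables remains worthwhile.

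**Conclusion.** The point holds as a minor defect in a stated rule. As written, Part A total and morning compliance are biased downward by 16.7 points per fully used unreturned wallet over 84 days, and by more with shorter exposure (25 points at 56 days, 50 at 28). The practical effect is on the compliance tables: a fully adherent completer with two wallets missing is reported below 80%.

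The effect on the Per-Protocol Population is possible but remote. For a fully adherent full-course patient it takes four of six wallets (three if the last dose is on Day 81 to 83 and all three were fully used). Fewer suffice with early termination or genuine non-adherence, and case review comes first. SAP 3.4.1.2 treats the Per-Protocol analysis as a sensitivity analysis, so the primary ITT result does not change, and Part B is not touched.

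This rests on the literal reading of the denominator, on missing wallets having been used in full, on the inferred wallet split for the by-visit examples, and on even intake for the non-adherence examples. How many wallets were unreturned, and what SAP V1.0 applied, are unknown.

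**What to change.** - In SAP 3.3.7, limit the Part A expected tablets, total and morning, to the days covered by returned wallets. Set compliance to missing if no wallet was returned.
- In the final Part A compliance tables, report the number of unreturned wallets beside the compliance figures.
- Confirm which denominator SAP V1.0 applied.
- Leave the Part A Per-Protocol Population as fixed. State whether any exclusion rested on unreturned wallets. If one did, show the Per-Protocol result with those patients included, labelled as a post hoc check.

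The cost is a short change to the SAP text and a small programming change to tables that are still to be issued. The downside is that compliance would then describe only the accounted-for days, which is why the count of unreturned wallets should stand next to it.
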